#### Treatment Plan: carfilzomib/romidepsin/lenalidomide Phase Ila

The phase IIa portion is planned to include 20 patients. Each disease cohort, B-and T-cell lymphoma, will have 10 patients. Patients treated at MTD in the phase Ib cohort (if measurable disease at enrollment) will be included towards the 20 patient total in the phase IIa. The MTD has been determined to be dose level 1; 8 mg/m² romidepsin on days 1 and 8, 15 mg lenalidomide from days 1 - 14, and 36 mg/m² carfilzomib on days 1 and 8. The phase IIa cohort will be evaluated both collectively and by disease subtype.

Patients that have received long-term therapy (greater than one year) with response will be allowed to have their schedule modified to allow less frequent dosing per investigator and primary investigator discretion.

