#### 9.5 **Dose Continuation, Modification and Interruption**

Subjects will be evaluated for AEs at each visit with the NCI CTCAE v4.0 used as a guide for the grading of severity. DLTs as defined will be tabulated in cycle 1 of phase Ib and cycles 1-4 of the phase Ila portion of the study. The toxicity decision rule for the Ila portion is described in Section 14.0. The sections below describe dose reduction steps, instructions for initiation of a new cycle of therapy and dose modifications during a cycle of therapy. Of note, if patient's experiences a greater than 10% change in body weight, dose of romidepsin should be adjusted accordingly. Doses do not need to be adjusted for less than 10% changes in body weight.

# 9.5.1 Instructions for Dose Modifications or Interruption During Phase 1 Cycle 1

There will be no dose reductions in cycle 1 phase 1. Inability to meet treatment criteria will result in holding the dose.

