#### 14.0 BIOSTATISTICS

The standard dose-escalation scheme for this study is as follows. Patients will be accrued to the study in cohorts of 3. For any given dose an initial cohort of 3 patients will be treated at that dose. The dose level will be escalated if none of the 3 patients exhibits any DLT in the first cycle as defined above. If a DLT is observed in one patient, an additional cohort of 3 patients will be treated at that dose. The dose will be escalated if none of the additional 3 patients exhibits any DLT. Dose-escalation stops and the previous dose will be considered the MTD if 2 or more patients have a DLT. If the previous dose level has been administered to only 3 patients, an additional 3 patients will be enrolled to confirm the result. For this design the probability of escalation is as follows:

True toxicity rate	5%	10%	15%	20%	25%	30%	40%	50%
Probability of escalation	0.97	0.91	0.81	0.71	0.60	0.49	0.31	0.17

Dose escalation will start with dose level 1. A dose level -1 is also added to the design to ensure a minimum level of toxicity (we expect this dose level will be quite tolerable for patients based on the phase I data of romidepsin and lenalidomide). The maximum number of patients needed for this dose escalation design is 30. We estimate accrual to be 2 patients per month. Patients with measurable disease treated at MTD in the phase Ib will be analyzed in phase Ila to further characterize the toxicity of carfilzomib, romidepsin and lenalidomide in combination at the MTD determined by phase Ib. In phase IIa, we plan to enroll patients so that the total number of patients enrolled in each disease type cohort (B-cell lymphoma and T-cell lymphoma) will include 10 patients at the MTD. We estimate accrual to be 1 patient per month in each disease type cohort. To consecutively monitor the safety primary endpoint in the phase IIa portion, we will employ a sequential probability stopping rule for the predefined DLT in the phase lb portion of cycles 1-4. This stopping rule specifies that the study will be terminated if DLT occur in: ≥3/first 6; ≥6/first 12; or if more than 10 patients when the last (20th) evaluable patient has completed the trial have any DLT. This rule has the following stopping probability:

True toxicity rate	5%	10%	15%	20%	25%	30%	35%	40%	50%
Stopping prob.	0.002	0.016	0.049	0.104	0.184	0.289	0.413	0.548	0.797
C									

e

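### Phase IIa stopping rule: the text stops above 10 DLTs in 20, but the tabulated stopping probabilities are those of 10 or more in 20

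*Combined protocol and SAP*

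**What the plan says.** Section 14.0 (Biostatistics) sets the safety monitoring for phase IIa: "we will employ a sequential probability stopping rule for the predefined DLT in the phase lb portion of cycles 1-4". The first two boundaries are written as inclusive: "This stopping rule specifies that the study will be terminated if DLT occur in: ≥3/first 6; ≥6/first 12". The third is written as a strict inequality: "or if more than 10 patients when the last (20th) evaluable patient has completed the trial have any DLT". The nine-column table is then introduced with "This rule has the following stopping probability" and prints 0.002, 0.016, 0.049, 0.104, 0.184, 0.289, 0.413, 0.548 and 0.797 for true toxicity rates of 5, 10, 15, 20, 25, 30, 35, 40 and 50%.

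The denominator is not in doubt. The phase IIa treatment plan in Section 9 says "The phase IIa portion is planned to include 20 patients". The final boundary is not restated anywhere else. Section 9.5 (Dose Continuation, Modification and Interruption) only points back, saying that the phase IIa toxicity decision rule "portion is described in Section 14.0".

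**The concern.** Read literally, the sentence stops the study at 11 or more DLTs in 20, while the table appears to have been computed for 10 or more. If so, the operating characteristics shown to readers of the protocol are not those of the rule they accompany.

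Safety and toxicity are the primary endpoint of phase IIa (Section 2.1), and this is its only formal toxicity stopping rule. If exactly 10 of 20 patients have a DLT and neither earlier boundary was crossed, the sentence says the study is not terminated and the tabulated design says it is. Whoever applies the rule would have to choose between them at that point.

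**Working it through.** **Inputs.** From Section 14.0: looks at 6, 12 and 20 evaluable patients; boundaries of 3 or more at the first look and 6 or more at the second; a final boundary of 11 or more as written; and the nine printed probabilities. Patients are treated as independent with a common DLT probability p.

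**Method.** Exact binomial recursion. At each look, add the probability of every path at or above the boundary to the stopping probability, and carry only the remaining paths forward.

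**Worked case, p = 0.5.** Every outcome sequence is equally likely, so the paths can be counted.

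- Look at 6: 0, 1 or 2 DLTs arise in 1 + 6 + 15 = 22 of 64 ways. Stopping probability: 42/64 = 0.6563.
- Look at 12: from 0, 1 or 2 DLTs, a total of 6 or more needs at least 6, 5 or 4 in the next six patients (1, 7 or 22 ways). Stopping paths: 1×1 + 6×7 + 15×22 = 373 of 4,096 = 0.0911. Cumulative: 0.7473.
- Paths still open at 12, by total DLTs: 396 with 5, 360 with 4, 200 with 3, 66 with 2, 12 with 1 and 1 with 0 (1,035 in all).
- Last eight patients, exactly 10 in total: 396×56 + 360×28 + 200×8 + 66×1 = 33,922 of 1,048,576 = 0.0324.
- Last eight patients, 11 or more in total: 396×37 + 360×9 + 200×1 = 18,092 of 1,048,576 = 0.0173.

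The rule as written therefore gives 0.7473 + 0.0173 = 0.7646. With 10 or more it gives 0.7646 + 0.0324 = 0.7969, which is the printed 0.797 after rounding.

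**The gap at any rate.** The two versions differ only in the paths with exactly 10 DLTs and no earlier stop, so the difference is 33,922 × p^10 × (1 − p)^10. At p = 0.4 this is 33,922 × 0.24^10 = 0.0215.

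**All nine cells:**

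| True rate | Printed | 10 or more of 20 | As written (11 or more) | Gap between versions, points |
|---|---|---|---|---|
| 5% | 0.002 | 0.0022 | 0.0022 | <0.01 |
| 10% | 0.016 | 0.0160 | 0.0160 | <0.01 |
| 15% | 0.049 | 0.0486 | 0.0485 | <0.01 |
| 20% | 0.104 | 0.1041 | 0.1037 | 0.04 |
| 25% | 0.184 | 0.1844 | 0.1826 | 0.18 |
| 30% | 0.289 | 0.2887 | 0.2831 | 0.57 |
| 35% | 0.413 | 0.4128 | 0.4002 | 1.26 |
| 40% | 0.548 | 0.5478 | 0.5263 | 2.15 |
| 50% | 0.797 | 0.7969 | 0.7646 | 3.24 |

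With 10 or more, the largest departure from the printed values is 0.0004, which is rounding. As written, the first four cells agree at three decimals and the last five do not.

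**Other explanations tried.** A final boundary of 9 or more gives 0.848 at 50%, and no final look gives 0.747; neither fits. With looks fixed at 6, 12 and 20, 160 boundary sets were searched (2–5 of 6, 4–8 of 12, 7–14 of 20), and only 3, 6 and 10 matched all nine cells. A wider search that also varied the look sizes (5–7, 10–13, 18–21) found no other match; the next best set missed by 0.004. Checking after every patient instead of at the three looks changes nothing, because reaching a boundary count early means it is also reached at that look.

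**The neighbouring table.** The 3+3 escalation probabilities in Section 14.0, (1 − p)^3 + 3p(1 − p)^5, come out at 0.973, 0.906, 0.814, 0.709, 0.600, 0.494, 0.309 and 0.172, as printed to two decimals. The mismatch is confined to the phase IIa rule.

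**The case against.** The arithmetic is not in dispute; the weight is. Up to a 20% true rate the table is unchanged at three decimals, and the gap never exceeds 3.3 points over the tabulated range. From either version a reader would conclude that the rule stops about 10% of the time at a 20% rate, a little over half the time at 40%, and between three quarters and 80% at 50%. The looks at 6 and 12, which both versions share, supply 0.519 of the stopping probability at 40% and 0.747 at 50%. The final boundary is assessed only once the 20th evaluable patient has finished, so no accrual to the 20 is left to halt.

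All of this stands, and it limits the importance of the point. It does not remove it. The final look still decides whether the study is formally terminated and how the regimen's toxicity is judged. Patients may also still be on treatment then, because Section 9.3 continues therapy until progression, unacceptable toxicity, patient or physician choice, or study closure. For that look alone the choice matters: it adds 0.0286 at 40% and 0.0496 at 50% under 10 or more, against 0.0071 and 0.0173 under the written wording. These are small probabilities, so the ratio should not be used to enlarge the finding.

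**Conclusion.** The concern holds. The printed stopping probabilities are those of 3 or more of 6, 6 or more of 12 and 10 or more of 20, not those of the written rule. The table overstates the written rule's stopping probability by about 0.2, 0.6, 1.3, 2.2 and 3.2 percentage points at true rates of 25, 30, 35, 40 and 50%, and by a negligible amount at 20% or below. Termination is decided differently in one outcome only: exactly 10 of 20 with no earlier stop.

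The calculation assumes independent patients with a common DLT probability and 20 evaluable patients. The agreement across all nine cells identifies the boundary used for the table, but it does not show whether the sentence or the table reflects the intended design; the documents leave that open. It should be fixed because it concerns the primary safety rule and costs almost nothing to correct.

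**What to change.** The sponsor should decide which final boundary was intended and make the sentence and table in Section 14.0 agree. There are two ways to do so:

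- Reword the final boundary as 10 or more of 20, in the same inclusive form as the first two, and leave the table as it is.
- Keep the present wording and replace the last five cells (25, 30, 35, 40 and 50%) with 0.183, 0.283, 0.400, 0.526 and 0.765.

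The cost is a few words or five table cells. Sample size, accrual and the boundaries at 6 and 12 patients do not change, and Section 9.5 needs no edit because it only refers to Section 14.0.

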# 15.1 RESEARCH PARTICIPANT REGISTRATION AND RANDOMIZATION PROCEDURES

# 15.2 Research Participant Registration

Confirm eligibility as defined in the section entitled Inclusion/Exclusion Criteria. Obtain informed consent, by following procedures defined in section entitled Informed Consent Procedures. During the registration process registering individuals will be required to complete a protocol specific Eligibility Checklist. The individual signing the Eligibility Checklist is confirming whether or not the participant is eligible to enroll in the study. Study staff are responsible for ensuring that all institutional requirements necessary to enroll a participant to the study have been completed. See related Clinical Research Policy and Procedure #401 (Protocol Participant Registration).

.

# 15.1. Registration for Participating Sites

Central registration for this study will take place at MSK.

To complete registration and enroll a participant from another institution, the site must contact the MSK study coordinator to notify him/her of the participant registration.

The following documents must be sent to the MSK study coordinator for each enrollment within 24 hours of the informed consent form being signed:

- The completed or partially completed MSK eligibility checklist
- The signed informed consent and HIPAA Authorization form
- Supporting source documentation for eligibility questions (e.g. labora tory results, pathology report, radiology reports, MD notes, physical exam sheets, medical history, prior treatment records, and EKG report).

Memorial Sloan Kettering Cancer Center IRB Number: 14-179 A(6)
Approval date: 12-Dec-2017

Administrative Update 1:06-Dec-2018

Upon receipt, the MSK study coordinator will conduct an interim review of all documents and will associate the participant to the study in MSK"s Clinical Trials Management System (CTMS). The participant will be assigned a protocol participant number in CTMS. This number will be relayed back to the study staff at the registering participating site via e-mail and will serve as enrollment confirmation. The number is unique and must be written on all data and correspondence for the participant.

If the eligibility checklist is not complete or source documentation is missing, the participating site will be responsible for sending the completed registration documents within 30 days of the consent.

Once the external registration submission is complete, if the participating site IRB has granted approval for the protocol and the participating site is in good standing, the MSK study coordinator will fully register the participant in CTMS. The participating site will be notified by the MSK study coordinator when registration is complete.

#### 15.3 Randomization

There is no randomization in this study.

#### 16.1 DATA MANAGEMENT ISSUES

A MSK Research Study Assistant (RSA) will be assigned to the study. The responsibilities of the RSA include project compliance, data collection, abstraction and data entry, data reporting, regulatory monitoring, problem resolution and prioritization, and coordination of the activities of the protocol study team.

The data collected for this study will be entered into a secure electronic Case Report Forms (eCRFs) by the assigned MSK RSA (for MSK patients only). Source documentation will be available to support the computerized patient record.

#### 16.1.1 Data and Source Documentation for Participating Sites

Data

The participating site(s) will enter data remotely into electronic Case Report Forms (eCRFs) using the internet based system, Medidata Rave. Data entry guidelines have been generated for this study and site staff will receive database training prior to enrolling its first participant. The participating site PI is responsible for ensuring these forms are completed accurately and in a timely manner. A schedule of required forms is shown in section 16.0.3.

#### **Source Documentation**

Source documentation refers to original records of observations, clinical findings and evaluations that are subsequently recorded as data. Source documentation should be consistent with data entered into eCRFs. Relevant source documentation to be submitted throughout the study includes:

- Baseline measures to assess pre–protocol disease status (ex. CT, PSA, bone marrow)
- Treatment records
- Toxicities/adverse events of grades that meet study reporting requirements and have not been previously submitted with a SAE Report
- Response designation
- o Any other forms of source documentation required per protocol

Source documentation should include a minimum of two identifiers to allow for data verification. MSK will maintain the confidentiality of any subject-identifiable information it may encounter.

**16.1.2 Data and Source Documentation Submission for Participating Sites**Participating sites should enter data directly into Medidata Rave. Source documentation should be sent to MSK to the contact information provided by the MSK study coordinator. Submissions should include a cover page listing relevant records enclosed per participant.

# 16.1.3 Data and Source Documentation Submission Timelines for Participating Site

Data and source documentation to support data should be transmitted via MediData Rave according to following chart:

Time point	Data	Source Documentation		
Baseline	Within 24 hours of consent (see section 4.0)	Within 24 hours of consent (see section 4.0)		

Study Visits	Within 14 days of the study visit	Within 14 days of the study visit
Serious Adverse E vents	Within 3 days of event(see section 17.3); Updates to be submitted as available	Within 3 days of event (see section 16.1.1)

\*Toxicities/adverse events that meet reporting requirement as outlined in section 11.

# 16.1.4 Data Review and Queries for Participating Site Data

Research staff at MSK will review data and source documentation as it is submitted. Data will be monitored against source documentation and discrepancies will be sent as queries to the participating sites. Queries will be sent by MSK Research staff twice a month.

Participating sites should respond to data queries within 14 days of receipt.

# 16.2 Quality Assurance

Registration reports will be generated to monitor patient accruals and completeness of registration data. Routine data quality reports will be generated to assess missing data and inconsistencies. Accrual rates and extent and accuracy of evaluations and follow-up will be monitored periodically throughout the study period and potential problems will be brought to the attention of the study team for discussion and action.

#### 16.2.1 Quality Assurance for Participating Sites

#### Monitoring

Each data collection site will be monitored periodically by MSK. Monitoring visits will be conducted every 4-8 weeks, dependent upon the protocol and patient accrual and activity. The monitor and the participating site will identify a mutually agreeable time for each monitoring visit. At least 10 business days ahead of the visit, the monitor will send the site a notification letter that details the date and expectations of the visit. Monitoring may be conducted remotely or in-person. The monitor must be allowed access to all protocol regulatory and source documents to assess compliance with the protocol, federal regulations and GCPs. The monitor will assess all data for completeness of source documents and to confirm data being recorded in the eCRFs is accurate. If monitoring will be done remotely, sites must agree in advance to provide source documents as required. During onsite visits, the monitor will also inspect and review the facilities and investigational product storage area. The participating site will maintain accurate records of dispensing of study drugs for drug accountability. Drug accountability will be reviewed at monitoring visits. Study drug and bottles must be retained until the monitor performs drug accountability of the study drug(s).

The site Investigator(s) and/or an authorized member of the Investigator's staff should allow sufficient time during monitoring visits to discuss findings. The Investigator(s) or an authorized member of the Investigator's staff will make any necessary corrections during and between monitoring visits.

# **Auditing**

Each participating site accruing participants to this protocol may be audited by MSK for protocol and regulatory compliance, data verification and source documentation. Audits of selected participant records may be conducted on-site or remotely.

Each audit will be summarized and a final report will be sent to the PI at the audited participating site within 30 days of the audit. The report will include a summary of findings, participant-specific case review, recommendations on any performance and/or shortcomings and request for corrective action, when necessary. When corrective action is required, the participating site must reply within 45 days of receipt of the audit report with their corrective action plan.

# 16.1.2 Response Review

Since therapeutic efficacy is a stated primary objective, all sites participant"s responses are subject to review by MSK"s Therapeutic Response Review Committee (TRRC). Radiology, additional lab reports and possibly bone marrow biopsies and/or aspirates will need to be obtained from the participating sites for MSK TRRC review and confirmation of response assessment. These materials must be sent to MSK promptly upon request.

# 16.2 Data and Safety Monitoring

The Data and Safety Monitoring (DSM) Plans at Memorial Sloan Kettering Cancer Center were approved by the National Cancer Institute in September 2001. The plans address the new policies set forth by the NCI in the document entitled "Policy of the National Cancer Institute for Data and Safety Monitoring of Clinical Trials" which can be found at: http://cancertrials.nci.nih.gov/researchers/dsm/index.html. The DSM Plans at MSK were established and are monitored by the Office of Clinical Research. The MSK Data and Safety Monitoring Plans can be found on the MSK Intranet at: http://inside2/clinresearch/Documents/MSKCC%20Data%20and%20Safety%20Monitoring%20Plans.pdf.

There are several different mechanisms at MSK by which clinical trials are monitored for data, safety and quality. There are institutional processes in place for quality assurance (e.g., protocol monitoring, compliance and data verification audits,

therapeutic response, and staff education on clinical research QA) and departmental procedures for quality control, plus there are two institutional committees that are responsible for monitoring the activities of our clinical trials programs. The committees: Data and Safety Monitoring Committee (DSMC) for Phase I and II clinical trials, and the Data and Safety Monitoring Board (DSMB) for Phase III clinical trials, report to the Center's Research Council and Institutional Review Board.

During the protocol development and review process, each protocol will be assessed for its level of risk and degree of monitoring required. Every type of protocol (e.g., NIH sponsored, in-house sponsored, industrial sponsored, NCI cooperative group, etc.) will be addressed and the monitoring procedures will be established at the time of protocol activation.

# 16.3 Regulatory Documentation

#### **Site Activation**

Prior to implementing this protocol at MSK, the protocol, informed consent form, HIPAA authorization and any other information pertaining to participants must be approved by the MSK Institutional Review Board/Privacy Board (IRB/PB). There will be one protocol document and each participating site will utilize that document.

The following documents must be provided to MSK before the participating site can be initiated and begin enrolling participants:

- Participating Site IRB approval(s) for the protocol, appendices, informed consent form and HIPAA authorization
- Participating Site IRB approved informed consent form and HIPAA authorization
- Participating Site 1572
- Conflict of Interest forms for Participating Site Investigators on the 1572
- Participating Site IRB membership list
- Participating Site IRB"s Federal Wide Assurance number and OHRP Registration number
- Curriculum vitae and medical license for each investigator and consenting professional
- Documentation of Human Subject Research Certification training for investigators and key staff members at the Participating Site
- Documentation of Good Clinical Practice (GCP) training for the PI and co-PI at each participating site.
- Participating site laboratory certifications and normals

Upon receipt of the required documents, MSK will formally contact the site and grant permission to proceed with enrollment.

